1.1 Background

Please refer to the protocol for a thorough account of the rationale and background of this study.

1.2 Protocol Version and Amendments

Study 21767/EPI VITRAKVI, v 1.0, 27 JULY 2021.

2. Study Objectives

The primary objective of this study is:

- to compare the time to medical treatment failure (defined as: next systemic treatment or mutilating surgery or radiation therapy or death due to any cause) between larotrectinib and

¹ SCOUT study, a Phase I/II study of the oral tropomyosin receptor kinase (TRK) inhibitor larotrectinib in pediatric patients with advanced solid or primary central nervous system tumors – international clinical study.

standard of care in IFS patients using externally-controlled comparison performed with phase I/II SCOUT study and eligible external historical cohort(s).

The secondary objectives of this study include the comparison of:

- Treatment outcomes (next systemic treatment, mutilating surgery, radiation therapy, death due to any cause),
- Treatment discontinuation rates due to toxicity.

Exploratory endpoints include:

- Progression-free survival (PFS): defined as the time (months) from the start of treatment to the date of first observed disease progression (radiological or clinical, whichever is earlier) or death due to any cause, if death occurs before progression is documented.
- Overall response rate (ORR): defined as the proportion of patients with a best overall response of complete response (CR) or partial response (PR) assessed by investigators.
- Disease control Rate (DCR): defined as the proportion of patients with a best overall response of CR, PR, or Stable Disease (SD).

3. Study Design

This study is a retrospective observational externally-controlled study. Data from patients with IFS within the following the two groups will be compared:

- From the international phase I/II clinical trial called 'SCOUT' conducted in a pediatric population (up to 21 years old) with advanced solid or primary central nervous system (CNS) tumors. Data are collected via electronic case report forms (eCRFs) completed by the investigators during the study conduct in each site.
- External historical control cohorts including:
 - *Institut Curie* database.
 - Database from the *Cooperative Weichteilsarkom Studiengruppe* (CWS, Germany).

3.1 SCOUT study

The pediatric subgroup of patients from both phase I and II of the SCOUT study, having IFS, or with other STS for complementary analyses described in [sections 5.1.1](#) and [5.1.2](#), will form the larotrectinib population in the analysis.

3.1.1 Phase 1 Dose Escalation and Dose Expansion

Phase 1 is a sequential-cohort dose escalation study designed to identify the maximum tolerated dose (MTD) through incidence and characterization of DLT. The adverse events (AE) defining dose limiting toxicity (DLT) are defined in integrated clinical study protocol (CSP) amendment, version 12.0, section 3.1.1.4.

Larotrectinib is administered twice daily (BID) in either an oral liquid or capsule form. Escalation in Phase 1 was to proceed through 5 planned dose levels or until the MTD was reached. When the optimal dose was thus identified, a Phase 1 expansion cohort of up to 18 patients was recruited to further

define the safety profile. Further details on the design of Phase 1 can be found in the integrated CSP amendment.

Individual patients will continue daily larotrectinib dosing until progressive disease (PD), unacceptable toxicity, or other reason for treatment discontinuation. All treated patients will undergo a safety follow-up visit at 28 days (\pm 7 days) after the last dose. Patients will be followed for long-term survival.

3.1.2 Phase 2

Phase 2 is an expansion study in 3 selected cohorts of pediatric patients with tumors bearing *NTRK* fusions: IFS, other extracranial solid tumors, and primary CNS tumors. At least 30 patients less than 18 years of age with a primary CNS tumor harboring an *NTRK* gene fusion, including 15 patients with high-grade gliomas (HGG) and another 15 patients with low-grade gliomas (LGG) were planned for enrollment to satisfy the PIP commitment that would show larotrectinib as a safe and effective treatment with significant anti-tumor activity and durable clinical benefit in children with a primary CNS tumor.

The Phase 2 study structure consists of screening, the treatment period, safety follow-up, and long-term follow-up until the study is closed. On-going safety (referred to as the “active safety follow-up” and described in integrated CSP amendment, version 12.0, section 7.6.1), survival, and subsequent anticancer therapies will be assessed during the long-term follow-up.

Larotrectinib is administered as an oral capsule or a liquid formulation at the recommended dose determined in Phase 1 (100 mg/m²; not to exceed 100 mg BID). Cycles are 28 days of continuous BID dosing. Patients undergo periodic radiologic evaluation and ongoing safety assessments as outlined in the protocol. Individual patients will continue daily larotrectinib dosing until PD, unacceptable toxicity, or other reason for treatment discontinuation, as outlined in integrated CSP amendment, version 12.0, section 6.4.

Patients with locally advanced disease and a response of at least a partial response (PR) for a period of one year after PR is initially confirmed may have their larotrectinib treatment withheld, a “wait and see” period, after discussion with the Sponsor. Patients with LGG and a response of stable disease (SD) for a period of at least 2 years after SD is initially confirmed, may similarly have their larotrectinib treatment withheld. Patients in the “wait and see” period will continue to undergo periodic radiologic evaluation and ongoing safety assessments as outlined in section 7.8 of the protocol. If a patient in this “wait and see” period is noted to have evidence of radiographic disease progression, the patient may restart larotrectinib. At the time of larotrectinib re-initiation, the patient will restart all per protocol assessments as delineated for patients on active treatment. Patients who reinitiate larotrectinib treatment are permitted to have their larotrectinib treatment stopped again.

Patients who undergo surgical resection resulting in negative margins may have their study treatment stopped and continue to undergo periodic radiologic evaluation and ongoing safety assessments as outlined in section 7.7 of the protocol. These patients are permitted to restart study treatment, if they experience PD, after discussion with the Sponsor. At the time of larotrectinib re-initiation, the patient will start all assessments per protocol as delineated for patients on active treatment.

3.2 External Cohorts

The choice of the control cohorts constituting the comparator arm of the study is not arbitrary. The non-arbitrary choice of the data sources to constitute the control cohort has been ensured by a comprehensive review of the existing relevant databases in France and internationally, notably based on a systematic literature review (SLR). After screening for full texts, 11 studies were included for data extraction. All these studies were critically reviewed against pre-defined criteria, validated by a scientific committee (Bayer study team, clinicians, methodologists, Institut Curie), to select cohorts of patients who present characteristics closest to those included in the SCOUT study and with sufficient methodological quality in order to be deemed appropriate for use as an external control arm to the SCOUT trial. All the studies identified within this SLR presented shortcomings on one or more parameters. However, two multicenter studies (Orbach et al. 2016 and Sparber-Sauer et al. 2020) had a lower risk of bias (ROBINS-I tool), especially as patient recruitment was prospective and had advanced IFS patients and minority of metastatic IFS patients. Both the studies reported longitudinal clinical efficacy data.

The Curie Institute database is the only database available in France describing French pediatric patients with IFS or STS harboring a *NTRK* gene fusion. Patient-level data contained in this cohort may provide useful information in the management of these patients. The Curie database will be augmented with data on IFS pediatric patients emanating from CWS. The two data sources will be pooled as a single comparator group for larotrectinib patients from the SCOUT trial, in order to address the request from HAS for further comparative analysis on larotrectinib treatment.

Despite those two studies had methodological limitations, among the 11 studies reviewed they are the most suitable to be considered as valid external control arm.

4. General Statistical Considerations

All issues concerning patient eligibility, data consistency checks, permissible data modifications, and coding of medical terms and concomitant medication will be described in detail in the Data Management Plan.

Sample Size and Power Considerations

The number of patients available is quite small, and no formal hypothesis and power calculations are considered for this study.

We can calculate the power for the comparison of two groups under a Cox Proportional Hazards Model, with the following applicable formula ([Error! Reference source not found. 2006](#))[1]:

$$\text{Power} = \Phi \left(\frac{\sqrt{km}|\text{IRR}-1|}{k \times \text{IRR}+1} - z_{1-\alpha/2} \right)$$

where m = expected total number of events over both groups

$$= n_1 p_E + n_2 p_C$$

n_1, n_2 = number of participants in experimental (E) and control (C) groups

k = n_1/n_2 (ratio of participants in E versus C groups)

p_C = probability of failure in group C over time period of study

p_E = probability of failure in group E over time period of study

IRR = underlying hazard ratio

[figure not shown]
$z_{1-\alpha/2}$ is the $100(1-\alpha/2)$ -th percentile of the standard normal distribution

Φ is the CDF of $N(0,1)$

The power calculations provided in the protocol assumed 35 IFS patients and probabilities of failure equal to 0.04 and 0.19 in SCOUT and the external historical control cohorts, respectively [Orbach (2020)]. Even with a strong treatment effect (hazard ratio (HR)=0.25), the power can only reach 49%, as further additions to the control cohort lead to smaller increases in power as the two groups become increasingly unbalanced. Therefore, having a powered study seems unfeasible.

Figure 1: Representation of the study power in function of the number of patients included in the comparator arm (control) for different hazard ratios

$nE=35$ (number of patients in the experimental group (treated with larotrectinib)

$pE=0.04$ (probability of failure in the experimental group during the study)

$pC=0.19$ (probability of failure in the control group during the study) (2) Orbach 2020(2))

$RR=0.5$ to 0.2 (risk ratio)

$\alpha=0.05$ (type I error)

Patients from SCOUT study will be taken from 20 July 2021 cut-off, using EPAS6 and ISAS1 subsets. EPAS6 is defined as those patients who were either in the primary analysis set on which approval of larotrectinib was based (N=55), or who satisfied the following conditions:

- NTRK Fusion Analysis Set
- Not CNS Primary Tumor
- Response evaluation criteria in solid tumors (RECIST) measurable disease at baseline
- First Dose Date on or prior to 19 January 2021

The ISAS1 subset extends the first dose date window of EPAS6 to on or prior to 20 July 2021.

As of the 20 July 2021 cut-off, there are 49 SCOUT IFS patients available for analysis. The pooled external cohorts from Curie and CWS will comprise N=42. Therefore, the power calculations in the protocol can be updated with current information on sample size as follows:

- N=49 IFS patients for SCOUT
- N=42 for pooled external control cohorts
- pE=0.04 (probability of failure in SCOUT) and pC=0.19 (probability of failure in control) per protocol assumptions
- Optimistic scenario of a strong treatment effect (HR=0.25)
- Power=51%
- Power cannot exceed 62.9% for N=49 for SCOUT and an unlimited number of subjects in the external arm

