9.2.3.2 Selection criteria for patients

- Inclusion criteria:

The inclusion criteria listed below are in line with those of the SCOUT study in terms of patients and disease characteristics:

- Age \leq 21 years old.
- Locally advanced or metastatic IFS.
- Patients with available information on clinical, radiological characteristics of their tumor, therapies administered and outcomes.
- Patients receiving larotrectinib in the SCOUT trial.

- Patients receiving at least chemotherapy-based regimen in the external historical control cohort(s).
- No opposition from the patients and/or representatives for data use.
- Exclusion criteria:
 - Patients treated with TRKi in the external historical control cohort(s).
 - Patients with documented absence of *NTRK* gene fusion:
 - Formal identification of *NTRK* gene fusion has not been retained as an inclusion criteria as the information might be missing from the databases used to constitute the external historical control cohort(s). Given the rarity of the condition and the anticipated small sample size, the study will authorize the inclusion of patients with unknown *NTRK* gene fusion status to maximize sample size while there is a limited risk of introducing a bias, as *NTRK* fusion is almost pathognomonic in IFS ([Orbach 2016](#)).
 - Patients participating in an investigational program with interventions outside of routine clinical practice.
- Population sampling strategy:

The study population will comprise all IFS patients in the SCOUT study and the eligible external historical cohort(s) (including at least the *Institut Curie* database) with a diagnosis of locally advanced or metastatic IFS regardless of their refractory or relapsed status, i.e. including treatment-naïve patients to avoid further reducing the sample size.

The choice of the study population has mainly been driven by feasibility/sample size considerations, in order to be able to perform a comparison based on a minimal number of patients.

In addition, the IFS population will also include patients with advanced or metastatic CMN since the histopathological characteristics of these tumors are very close to those of IFS, as mentioned in the WHO sarcomas classification ([Kallen and Hornick 2020](#)). Moreover, the presence of the same fusion transcript as in IFS is identified in the cellular form of CMN ([Thebaud 2012](#)).

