4.6 Definition of Derived Variables and Subgroups

A subgroup analysis will be performed on the primary endpoint for patients who take larotrectinib as second-line therapy or are treated with second-line or higher systemic therapy in the external historical cohorts. A similar subgroup analysis will be conducted for comparing first line Larotrectinib patients versus external controls taking at least 1 line of therapy. This is described fully in [section 6.2.5](#).

5. Analysis Sets

All analyses will be performed on the Full Analysis Set (FAS), comprising patients in the SCOUT trial, or the pooled population of Institut Curie and CWS.

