5.1 Assignment of Analysis Sets

FAS

A patient will be included in the FAS if the patient has taken at least one dose of larotrectinib for SCOUT study, or has fulfilled the eligibility criteria for inclusion into the pooled external cohorts and has initiated chemotherapy.

All analyses detailed below will be repeated separately for two populations of FAS:

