5.1.1 IFS Population

- Age \leq 21 years old
- Locally advanced or metastatic IFS
- Patients receiving
 - larotrectinib in the SCOUT trial, or
 - receiving at least one chemotherapy-based regimen in the external historical control cohorts.

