6.3.7 Overall Response Rate

ORR is defined as the proportion of patients with a best overall response of CR or PR assessed by investigators.

Summary statistics for ORR with 95% 2-sided exact binomial confidence intervals will be reported. In addition, a weighted analysis will be conducted. The binary response outcome (ORR), is regressed on group indicator (larotrectinib, comparator) using a logistic regression model, incorporating the IPTW weights calculated for the primary endpoint. Standard errors are calculated using a robust sandwich estimator. The odds ratio comparing larotrectinib to comparator, with 95% confidence interval, will be provided. A corresponding odds ratio will also be reported for the unweighted samples.

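### Measurable disease is an entry condition for most SCOUT routes but not for controls, and the SAP does not say how ORR and DCR handle a control with no measurable tumour

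*SAP*

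**What the plan says.** **SCOUT arm.** SAP section 4 draws patients from EPAS6 and ISAS1. A patient enters EPAS6 if "either in the primary analysis set on which approval of larotrectinib was based (N=55), or who satisfied the following conditions"; one of those conditions is "Response evaluation criteria in solid tumors (RECIST) measurable disease at baseline". ISAS1 only extends the first-dose window. SAP 5.1 describes the same arm more loosely: "A patient will be included in the FAS if the patient has taken at least one dose of larotrectinib".

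**Control arm.** SAP 5.1.1 asks for age up to 21, "Locally advanced or metastatic IFS", and "receiving at least one chemotherapy-based regimen in the external historical control cohorts". Protocol 9.2.3.2 adds "Patients with available information on clinical, radiological characteristics of their tumor, therapies administered and outcomes". That criterion concerns whether data exist; it does not require measurable tumour when chemotherapy starts.

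**Endpoints.** SAP section 5 runs every analysis on the FAS. In SAP 6.3.7, "ORR is defined as the proportion of patients with a best overall response of CR or PR assessed by investigators". SAP 6.3.8 defines DCR in the same way with SD added. Both are reported as weighted and unweighted odds ratios. SAP 4.3.2 rules out imputing missing tumour response evaluations. The PFS rules in SAP 6.3.6 provide for patients with no baseline tumour assessment; 6.3.7 and 6.3.8 have no counterpart.

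**The concern.** A patient with no measurable tumour at baseline cannot record a partial response. Outside the approval set, the SAP screens such patients out of SCOUT, but nothing written screens them out of the controls. Part of any ORR difference could then reflect who was able to respond.

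Such controls are plausible. SAP 6.1.2 lists the number of previous surgical resections as a baseline variable, and protocol 9.3.4 collects resection margins and records stage at diagnosis. In the European series described in protocol 7.8, 64 patients had surgery combined with chemotherapy; the order is not given. A child staged as locally advanced at diagnosis could therefore start chemotherapy after resection.

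Weighting offers only partial protection. Measurable disease is in neither propensity model in SAP 6.2.2. IRS group (both models) and prior surgery (full model only) are proxies. SCOUT IRS is derived from stage and is III or IV by construction (SAP 6.1.4), so an IRS I or II control would have no SCOUT counterpart. As its propensity score approaches zero, its stabilised weight approaches 42/91 = 0.46, so it is down-weighted but not removed. Trimming does not help, because SAP 6.3 confines the sensitivity analyses to the primary endpoint. The unweighted odds ratio has no protection.

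**Working it through.** **The plan's own figures.** The documents give no power or expected value for the ORR comparison. Two nearby figures reproduce:
- SCOUT IFS ORR (protocol 7.5.1, n=34): 32/34 = 94.1%, exact 95% CI 80.3% to 99.3%; stated 94% (80, 99).
- Power for the primary endpoint (SAP section 4): k = 49/42, expected events m = 49 × 0.04 + 42 × 0.19 = 9.94, HR 0.25, two-sided 5%. The SAP formula gives 50.7%; stated 51%.

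**Inputs for the illustration**
- SCOUT ORR 94%: protocol 7.5.1, July 2019 cut-off, earlier than the cut-off used here.
- Controls: 42 (SAP section 4).
- r, ORR among controls with measurable tumour: not given; assumed 70%, 80% or 94%.
- u, controls without measurable tumour: not given; assumed 0 to 8.

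**Such controls kept as non-responders.** Control ORR = r × (42 − u)/42, and OR = odds(0.94)/odds(control ORR), where odds(0.94) = 0.94/0.06 = 15.67.

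| u | Control ORR, r=70% | OR, r=70% | OR, r=80% | OR, r=94% |
|---|---|---|---|---|
| 0 | 70.0% | 6.7 | 3.9 | 1.0 |
| 2 | 66.7% | 7.8 | 4.9 | 1.8 |
| 4 | 63.3% | 9.1 | 6.0 | 2.7 |
| 8 | 56.7% | 12.0 | 8.5 | 4.9 |

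Example, r=70% and u=4: responders 0.70 × 38 = 26.6, odds 26.6/15.4 = 1.727, OR = 15.67/1.727 = 9.1. The last column has no true difference, so all of its odds ratio above 1 is artefact.

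**Same controls coded CR.** Control ORR = (r × (42 − u) + u)/42. With r=70%:
- u=2: 30/42 = 71.4%, OR 15.67/2.50 = 6.3
- u=4: 30.6/42 = 72.9%, OR 15.67/2.684 = 5.8
- u=8: 31.8/42 = 75.7%, OR 15.67/3.118 = 5.0

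The tilt now runs against larotrectinib.

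**Coded SD.** This is a non-response for ORR, so the table applies. For DCR it counts as disease control, so there the tilt runs towards the controls.

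**Left missing and dropped from the logistic model.** Control ORR stays at r and the OR at 6.7 (r=70%), whatever u is.

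**SCOUT count.** SAP section 4 gives 49 SCOUT IFS patients. The line-of-therapy table in SAP section 7 gives 19 + 32 = 51. At 51 versus 42 the power formula gives 51.9%, so the effect on power is small, but the analysis set is not pinned down.

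**The case against.** A reader might infer that these controls are counted as non-responders and that ORR is therefore biased towards larotrectinib. The documents do not support that as a statement of fact, for three reasons.

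- **Coding.** No rule says how such a patient is handled. The FAS denominator points towards non-response, but without imputation a blank response could drop out, and a tumour-free child who does not progress could be recorded as CR or SD. Direction depends on coding, and the case is weakest for DCR.
- **Existence.** Controls must have locally advanced or metastatic disease. SAP 6.1.4 equates these with IRS III and IV for SCOUT, and protocol 7.2 places chemotherapy mainly in unresectable tumours. Zero affected controls is a realistic outcome.
- **Importance.** ORR and DCR are exploratory, in a study with no formal hypothesis.

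All three stand, and they make the concern conditional. Two further objections stand in part. SAP section 4 leaves eligibility detail to the Data Management Plan, which is not available here and may contain a control rule; even so, the response denominator belongs in the SAP. The two SCOUT descriptions can be read together, with section 4 naming the source and 5.1 adding a dosing condition. On that reading 5.1 needs clarifying, but the counts of 49 and 51 still need reconciling.

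A reader might also extend the point to the primary endpoint. Nothing in the documents fixes a direction or size there.

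**Conclusion.** The one-sided selection rule is in the text; the bias is conditional. It arises only if some controls lacked measurable tumour at the start of chemotherapy and remain in the denominator. It favours larotrectinib on ORR if they are coded as anything other than CR, and runs the other way if they are coded CR. On DCR, either CR or SD reverses it.

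Under non-response coding, control ORR shrinks by the factor (42 − u)/42: 4.8% relative for u=2, 9.5% for u=4 and 19% for u=8. With 94% and 70% assumed, the odds ratio is inflated 1.17-, 1.35- and 1.78-fold. These are unweighted illustrations; r and u are assumptions, and with u=0 nothing changes. The point is worth correcting because different codings give different odds ratios and the SAP does not choose between them.

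**What to change.** 1. In SAP 6.3.7 and 6.3.8, analyse ORR and DCR in both arms among patients with documented measurable, or recorded gross, tumour at the index date. Apply the same rule to SCOUT patients who enter through the approval set.
2. State how not-evaluable and missing best responses are handled, and whether the primary-endpoint weights are kept or re-estimated in the restricted set.
3. Report the number excluded per arm, and show the all-FAS result alongside. If no control is affected, a reported zero settles the matter.
4. Do not use IRS III/IV as the only filter. Because SCOUT IRS is derived from stage, that filter would test the controls alone.
5. State in SAP 5.1 that the SCOUT FAS is the EPAS6/ISAS1 subset, and reconcile 49 patients with the 51 in the line-of-therapy table.

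The cost is some SAP wording and one baseline flag per patient, which depends on tumour status at chemotherapy start being recorded in the control databases. A few controls may be lost from two exploratory endpoints, and the ORR contrast may look less favourable to larotrectinib.
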